#### Clinical pathologic data:

- 1). Characteristics of epidemiology (Age, reproductive history, menstrual history, body parameters)
- 2). Diagnostic criteria (pathology, transvaginal ultrasonography or magnetic resonance image)
- 3) Semeiology and evaluative criteria (vision algetic standard (VAS); pictorial blood loss assessment chart (PBAC))
- 4) Surgical approach and perioperative reproductive techniques program
- 5) Medical treatment
- 6) Reproductive choices and fertility outcomes
- 7) Symptom improvement, quality and satisfaction of Life
- 8) Malignant transformation
- 9) Menopausal symptoms and Hormone therapy
- 10) Systematic assessment of the side effects

Picture 1. Network platform (NP) and database Building

- 2. Based on the database imformations, 30-month follow-up will be done for every patient, trying to analyze the problems below: 1) The diagnostic strategies for AM;2) Selection of therapeutic scheme;3) Etiology of AM and endometriosis;4)The study of histology, molecular and genetics about AM and endometrial receptivity.
- 3. The Follow-up visits is standardized, and the contents include :1) The therapeutic efficacy, complication and side-effect of different treatments;2)The fertility outcomes of different reproductive choices;3) AM &menopausal symptoms and hormone therapy; 4) Relevant issues among malignant transformation of AM.
- 4. According to the data above, intensive training courses about AM will be organized regularly, finally propeling the formation of Expert Consensus and Clinical Guidelines about AM which suitable to chinese conditions.

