#### D. STATISTICS ANALYSIS

Categorical data is analyzed by Chi-square test, and continuous data is analyzed by T test. If the baseline characteristics are similar, the chi-square test can be used directly to compare the incidence rates between the group of exposure and the group of non-exposure, to conclude if there is a correlation between the exposure factor and outcome. In a meanwhile, calculate the relative risk and 95% confidence interval in order to further illustrate the degree of correlation. In contrast, if the baseline characteristics of exposure group and non-exposure group are different, multiple factor linear regression should be used to control the

mixing factors. If there is no time variation in the data, logistic linear regression can be used to adjust the baseline characteristics of the groups which are different in the model. If there are time variations in the data, Cox linear regression should be used to adjust the baseline characteristics of the groups which are different in the model.

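### Section D adjusts for confounders only where the groups look different at baseline, and names no method for symptom or quality-of-life scores if these are repeated over follow-up.

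*Combined protocol and SAP*

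**What the plan says.** Section B describes a prospective multicentre observational cohort with 30 months of follow-up and contact at least every six months. Section C (item 3, on follow-up visits) lists among the contents "The therapeutic efficacy, complication and side-effect of different treatments". The recorded data in Section C include "Age, reproductive history, menstrual history, body parameters" (item 1), VAS and PBAC (item 3), and "Symptom improvement, quality and satisfaction of Life" (item 7).

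Section D is the only analysis text. It gives these rules:

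- As a general rule naming no outcome, "continuous data is analyzed by T test", and categorical data by the chi-square test.
- If baseline characteristics are similar, the chi-square test is applied directly to incidence rates, with a relative risk and 95% confidence interval.
- Otherwise, "if the baseline characteristics of exposure group and non-exposure group are different, multiple factor linear regression should be used"; the stated aim is to deal with confounding.
- Logistic regression (no time variation) and Cox regression (time variation) serve to "adjust the baseline characteristics of the groups which are different in the model".
- For data that vary over time, this is the only instruction: "If there are time variations in the data, Cox linear regression should be used".

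Section D does not define similar, different or time variation. It lists no covariates in advance and names no repeated-measures method.

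**The concern.** Women are not randomised to treatments, so confounding is the main threat to any comparison of efficacy. A rule that adjusts only for visible differences has two faults. First, a characteristic can be related to both treatment and outcome without its gap being conspicuous. Such gaps are easiest to miss in small treatment subgroups, and several in the same direction add up. Second, without a criterion or a list, two analysts with the same data could properly reach different covariate sets after seeing the baseline table. Section C says the results are meant to feed an expert consensus and clinical guidelines, so an analysis fixed in advance matters.

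A separate gap concerns repeated scores. Contacts at least every six months over 30 months mean at least 30/6 = 5 per woman. If VAS, PBAC or quality-of-life scores are taken at these contacts, they are correlated within a woman, and neither a t test nor single-visit linear regression handles that.

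**Working it through.** The plan gives no effect size, SD, error rate or power, so there is no figure of its own to reproduce. What follows illustrates the rule for a continuous outcome.

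**Assumptions, none set by the plan.** Outcome SD 1; no true treatment effect; *similar* means a baseline comparison with p>0.05; n = 200 per group (in the documents 200 is only the minimum per centre); baseline-to-outcome correlation r = 0.3/0.5/0.7.

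**How often a gap passes as similar.** se = sqrt(2/200) = 0.100, so an observed gap g passes if |g| < L = 1.96 × 0.100 = 0.196. With g ~ N(true gap, se²), a true gap of 0.10 SD passes in 83.0% of comparisons and one of 0.196 SD in 50.0%. With 100 per group, gaps of 0.1, 0.2 and 0.3 SD went unflagged in about 90%, 71% and 44% of simulated comparisons.

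**One baseline score, whole rule** (final-value t test if the gap passes, ANCOVA otherwise). Given g, the final-value difference has mean r·g and SD se·sqrt(1−r²). ANCOVA rejects at 5%. Whole-rule rejection = P(pass) × rejection among passing + P(flagged) × 5%.

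| True gap | Rejection among passing, r = 0.3/0.5/0.7 | Whole rule |
|---|---|---|
| 0 | 4.8/4.3/3.5% | 4.8/4.3/3.6% |
| 0.10 SD | 5.1/5.2/5.1% | 5.1/5.2/5.1% |
| 0.196 SD | 5.7/6.9/8.1% | 5.4/5.9/6.5% |

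For example, at 0.196 SD and r = 0.7: 0.5 × 8.1 + 0.5 × 5 = 6.55, or 6.5% before rounding of the inputs. Mean bias over the whole rule is at most about 0.04 SD. At 100 per group, simulated rejection peaked at 6.9%, against 4.5 to 5.2% when always adjusting.

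**Several characteristics.** Take five independent ones (the four in Section C item 1 plus a baseline score), each with a true gap of 0.10 SD, together explaining R² = 0.25 or 0.50 of outcome variance. Each slope is sqrt(R²/5) = 0.224 or 0.316.

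- Expected number left unadjusted: 5 × 0.830 = 4.15.
- Mean gap left in by one characteristic, with φ the standard normal density: 0.10 × 0.830 − 0.100 × [φ(0.96) − φ(2.96)] = 0.0830 − 0.0247 = 0.0583.
- Bias if all push the same way: 5 × 0.224 × 0.0583 = 0.065 SD, and 5 × 0.316 × 0.0583 = 0.092 SD.
- Simulated rejection: about 9% (R² = 0.25) and 13 to 14% (R² = 0.50). With random directions it is about 5 to 6%. Always adjusting gives about 5%.

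**Large groups.** Splitting 5,000 women equally (assumed) gives 2,500 per group and se = 0.028. A 0.10 SD gap then passes in only 5.8% of comparisons, so about 5 × 0.058 = 0.3 of the five stay unadjusted. Simulated bias is below 0.005 SD and rejection is 5.5 to 6.0%.

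**Limits of adjustment.** If groups differ by a stable gap G, ANCOVA keeps a bias of (1−r)·G (0.07/0.05/0.03 SD at G = 0.10), while a change score is unbiased. If instead the gap shrinks to r·G by follow-up, ANCOVA is unbiased and the change score is off by −(1−r)·G.

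**The case against.** - **Cox regression.** A reader might infer that the plan would apply Cox regression to repeated VAS, PBAC or quality-of-life scores. The text does not support this. The similar-or-different passage speaks of incidence rates and relative risk, so logistic regression without time variation and Cox with it read most naturally as fixed-time and time-to-event analyses of binary outcomes. Cox regression is suitable there. What stands is that no method is named for repeated scores, and their repetition is implied by Sections B and C rather than stated.
- **Size.** A reader might infer serious error inflation across the cohort. The figures do not show it. With one score the whole rule is close to nominal, and with 2,500 per group the bias is negligible. The larger figures need five gaps in one direction, which the documents do not establish.
- **The p>0.05 reading.** The plan names no baseline test; this threshold is supplied only to make the rule computable. The illustration also covers a continuous outcome, whereas the direct unadjusted test is written for incidence rates, and the effect on a relative risk is not quantified here.
- **Linear regression is already named.** That is so, and it is usable at a single visit. Its use still depends on the undefined trigger.

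None of this defends choosing covariates by how the baseline looks.

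**Conclusion.** The concern holds in a limited form. In a non-randomised comparison of treatments, adjusting only for characteristics that look different is an inferior way to select confounders, and it leaves the choice open until the data are seen. The statistical harm is modest and mainly a matter for small treatment subgroups. At an assumed 200 per group it runs from almost nothing with one score to a bias of 0.06 to 0.09 SD when five small gaps align. The case for change rests on pre-specification and accumulated small gaps, not on a demonstrated large error. The missing method for repeated scores is a separate gap, conditional on those scores being collected at the six-monthly contacts. Section D should be changed; confidence is moderate, because the size depends on assumptions that the documents do not settle.

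**What to change.** In Section D:

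1. Delete the trigger based on similar or different baselines. For each exposure-outcome question, fix a covariate list in advance and use it in the linear, logistic and Cox models however alike the groups look.
2. Draw the list from data already recorded: the characteristics in Section C item 1, the pre-treatment score where available, centre, and prior treatment or reproductive choices where they precede the exposure and bear on treatment selection. The questions on treatment, fertility, menopause and malignant transformation need separate lists.
3. Where events are few, keep the list short or use a propensity score or a penalised model.
4. For scores, use baseline-adjusted linear regression at one named visit, or a linear mixed model if they are repeated. State that Cox regression is for time-to-event outcomes.
5. Report a change-score analysis alongside, because neither it nor ANCOVA is unbiased under every kind of group difference.

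The cost is new wording and modest extra analysis; recruitment and treatment are unaffected. Under the assumed correlations, baseline adjustment also cuts variance against a final-value t test by r² = 9/25/49%. The downsides: data come from medical records (Section C item 1 of the technical route), so some women may lack a pre-treatment score; the mixed model assumes data are missing at random; and ANCOVA reduces but does not remove bias from stable group differences.

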# A. OBJECT

5000 women diagnosed of Adenomyosis(AM) with pathology or magnetic resonance image (MRI) will be enrolled from nationwide multicenter. Each center should recruite at least 200 patients.

— **PATHOLOGY**: Adenomyosis can be present diffusely throughout the myometrium, or confined to a discrete area. Upon sectioning the uterus, the myometrial wall appears thickened and often contains small hemorrhagic or chocolate colored areas representing islands of endometrial bleeding. The term cystic is used to describe either diffuse adenomyosis or adenomyomas for which with cysts >5 mm in diameter.

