### **B. STUDY DESIGN AND METHOD**

**—STUDY DESIGN:** A Prospective Multicenter Observational Cohort Study —**METHODS**:

**Period:**3 years, including 6 months for building up Network platform and database, 30 months for the follow-up with an interval of at least once every 6 months done for every patient and updating the database timely.

[figure not shown]

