## C. TECHNICAL ROUTE

1. **Build up database basing on the Network platform.** Licensed research centers recruite patients according to the consistent universal diagnostic criteria, and then extract and register clinical pathologic data from their medical records system after getting their informed consent. Limited sharing platform for the database entry would be built by expert network firms, making it available for sub-centers to access the database and download relevant data. Ultimately, on the premise of research results sharing, we could carry out clinical scientific research development and summary nationwide. [Picture 1.]

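### The plan compares exposed and non-exposed groups with baseline adjustment only and does not say when exposure is classified, so treatments begun after enrolment could be credited with event-free time that preceded them

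*Combined protocol and SAP*

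**What the plan says.** Section B describes "A Prospective Multicenter Observational Cohort Study", with "30 months for the follow-up with an interval of at least once every 6 months done for every patient". No treatment allocation is described. Entry is by diagnosis: Section A states that "5000 women diagnosed of Adenomyosis(AM) with pathology or magnetic resonance image (MRI) will be enrolled from nationwide multicenter", and Section C has centres "recruite patients according to the consistent universal diagnostic criteria".

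The data list in Section C covers surgery, perioperative reproductive techniques, medical treatment, reproductive choices and hormone therapy. Choice of therapy is one of the questions to be analysed. Item 3 of Section C says the follow-up visits cover "The therapeutic efficacy, complication and side-effect of different treatments" and "The fertility outcomes of different reproductive choices".

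Section D gives the analysis rule. If the groups are similar at baseline, "the chi-square test can be used directly to compare the incidence rates between the group of exposure and the group of non-exposure", with a relative risk and 95% confidence interval. If they differ, a regression model adjusts for the baseline differences. It is logistic when the data do not vary over time; when they do, "Cox linear regression should be used to adjust the baseline characteristics of the groups which are different in the model".

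The documents do not define time zero, the moment at which exposure is classified, or the handling of a start, stop or switch during follow-up. They mention no time-dependent exposure, landmark or new-user design.

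**The concern.** A cohort that enters on diagnosis can contain women who begin a treatment months later. To be counted as treated, such a woman must first reach the start date without the event. If she is then placed in the exposed group from enrolment, the time before her treatment becomes exposed time in which an event was impossible. Meanwhile, women who have the event early, before any treatment, fall into the non-exposed group. This is immortal-time bias. It comes from how person-time is allocated, so adjusting for characteristics measured at baseline leaves it in place.

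What is at stake is the treatment question itself. Section C says the results are meant to feed an expert consensus and clinical guidelines, and with 5000 women a spurious effect would come with a narrow interval.

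**Working it through.** **Inputs from the documents.** Follow-up is 30 months with visits at least every 6 months (Section B). The target is 5000 women (Section A). The target has no derivation, so there is no figure of the plan to reproduce; it serves here only as the simulated sample size. The documents give no event risk, treatment uptake or start timing. All of those below are assumptions.

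**Closed form with no treatment effect.** Let R be the 30-month event risk and S the share who would start treatment by 30 months if they stayed event-free. Both hazards are constant, and a start counts only if it precedes the event.

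- Event hazard λ = −ln(1−R)/30; start hazard μ = −ln(1−S)/30.
- Share ever treated: p = μ/(λ+μ) × [1 − (1−R)(1−S)].
- Share treated and later having the event: p − S(1−R).
- Risk in ever-treated = [p − S(1−R)]/p. Risk in never-treated = [R − p + S(1−R)]/(1−p).

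With R = 20% and S = 50%:

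- μ/(λ+μ) = 0.6931/(0.2231 + 0.6931) = 0.7565, so p = 0.7565 × (1 − 0.8 × 0.5) = 0.4539.
- Ever-treated: (0.4539 − 0.4000)/0.4539 = 0.0539/0.4539 = 11.9%.
- Never-treated: (0.2000 − 0.0539)/0.5461 = 0.1461/0.5461 = 26.8%.
- Relative risk = 11.9/26.8 = 0.44, although treatment does nothing.

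Over event risks of 5% to 60% and uptake of 10% to 70%, the same formula gives relative risks from 0.33 to 0.64.

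**Simulation with no treatment effect** (5000 women, 60 replicates per row). The fixed-exposure column counts anyone ever treated as exposed from enrolment. The last column uses the same data with time before the start counted as unexposed.

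| Event risk; uptake; start pattern | Fixed-exposure Cox HR | Null rejected at 5% | Time-dependent HR |
|---|---|---|---|
| 10%; 30%; constant rate over 30 months | 0.44 | 100% | 1.00 |
| 20%; 50%; constant rate over 30 months | 0.39 | 100% | 1.01 |
| 40%; 50%; constant rate over 30 months | 0.39 | 100% | 0.98 |
| 20%; 50%; uniform over 30 months | 0.34 | 100% | 1.00 |
| 20%; 50%; uniform within 12 months | 0.66 | 100% | 1.01 |
| 20%; 50%; uniform within 6 months | 0.80 | 93% | 1.00 |
| 20%; 50%; uniform within 1 month | 0.96 | 10% | 0.99 |
| 20%; 30% treated at entry, 50% uptake in the rest | 0.54 | 100% | 1.00 |
| 20%; 50% treated at entry, 30% uptake in the rest | 0.74 | 100% | 0.99 |

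A separate run of four constant-rate scenarios (risk/uptake 20/20%, 40/20%, 40/40% and 60/40%) gave fixed-exposure hazard ratios of 0.48, 0.47, 0.43 and 0.42. In the table, the time-dependent analysis rejected the null in 2% to 8% of replicates, which is compatible with 5% given only 60 replicates.

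**Exposure classified at enrolment only** (event risk 20%, 30% exposed, 200 replicates): hazard ratio 0.99, null rejected in 5.5%. Immortal time does not arise.

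**The case against.** The strongest objection is that the plan does not state the rule simulated above. A reader might infer from the two-group wording that Section D prescribes an ever-treated versus never-treated comparison. It does not. It refers to the baseline characteristics of the two groups, which can fairly be read as groups that already exist at baseline, and on that reading the bias is absent. This stands: the defect is an unstated exposure time and time zero, not a stated wrong rule. It does not dispose of the point. Classification at enrolment is not written either, and it would place later starters in the wrong group and ignore switches.

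Second, no section says that treatments begin or change during follow-up. Section C has the clinical data taken from medical records, and women diagnosed by pathology may have had surgery before entry. This also stands. Later starts remain a reasonable inference from entry at diagnosis, the absence of allocation, 30 months of follow-up, and reproductive choices and hormone therapy being among the follow-up topics.

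Third, a reader might take a hazard ratio near 0.4 as the expected size. That figure needs nobody treated at entry and starts spread across the whole period. The table shows the bias shrinking toward nothing as starts move to entry.

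Fourth, a reader might conclude that the bias always flatters treatment. It does so for adverse events. For desired events such as pregnancy, the same error makes treatment look as if it reduces or delays them. The mechanism concerns time-to-event outcomes for which treatment begun after the event is not counted. It does not carry over directly to repeated pain (VAS) or bleeding (PBAC) scores.

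**Conclusion.** The concern holds in a conditional form. Section D offers only a two-group test or a baseline-adjusted model and gives no valid handling for treatments begun after enrolment. Counting later starters as exposed from enrolment gives a false effect. Fixing exposure at enrolment avoids that, but misclassifies later starters and switchers.

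Under no true effect, the size runs from a hazard ratio of about 0.4 to 0.5 (0.34 in one scenario) when starts are spread over 30 months and nobody is treated at entry, to 0.96 when all starts fall within 1 month. It is about 1 when exposure is fixed at enrolment. If all starts fall within 6 months, one maximum visit interval, the hazard ratio is 0.80 and a true null was rejected in 93% of simulated cohorts of 5000. These figures rest on assumed event risks, uptake and start times. They show what the present wording allows, not what the study will find.

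The change should be made, because it is cheap and dates not captured prospectively may be hard to recover.

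**What to change.** In Section D, for every treatment that can start after enrolment, name one design per comparison and do not mix the two:

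- **Treated versus untreated.** Time zero is enrolment. Treatment enters the Cox model as a time-dependent covariate built from recorded start, stop and switch dates, and time before initiation counts as unexposed.
- **One treatment versus another.** Time zero is the start of each woman's index treatment (new-user design). State how women already on treatment at enrolment are handled.

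Restrict the chi-square test and relative risk to exposures already fixed at time zero. Where feasible, adjust for symptom scores updated at the 6-monthly visits. State that time-dependent exposure removes immortal time but does not by itself remove confounding by changing symptoms that prompt treatment.

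The cost is the revised wording, treatment start, stop and switch dates in the database, more programming and somewhat wider intervals.

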# E. QUALITY CONTROL MEASUREMENT AND RESULT PUBLICATION

- 1. Every center of the research possesses the competence of scientific research to conduct clinical studies. Special people from each center will be put in charge of the research and monitoring the whole procedure. The rights and interests, responsibility and obligation of all centers will be standardized with the research agreement.
- 2. The maintenance, secrecy and safety of Network platform and database will be guaranteed by Department of Obsterics and Gynecology, Peking Union Medical College Hospital.
- 3. Every center is responsible for the database building, and required to finish the prospective follow up for 200 patients at least.
- 4. The researchers' findings will be released in a paper published online.

# F. SOURCE(S) OF FUNDING

- 1. This study does not charge any fee to any patients.
- 2. The major cost of the study, a total of 300000 RMB, comes from the special financial funds set up by Chinese Medical Doctor Association Division of Gynecologic Endocrinology and Chinese Maternal and Child Health Association Division of Gynecologic Endocrinology.
